#### Adverse Events (AEs) to be reported for WF-1801

- **Grade 3:** Any **unexpected** adverse events (AEs) **grade 3** that have an attribution to the intervention of **Possible, Probable or Definite** should be reported.
- **Grade 4:** Any **unexpected** adverse events (AEs) **grade 4** should be reported.
- **Grade 5:** All adverse events (AEs) **grade 5** should be reported.

#### Methods and Timing of Reporting Adverse Events

**Please refer to the chart below for method(s) of reporting.**

- **All reportable adverse events** will be reported to the Wake Forest NCORP Research Base using REDCap Adverse Event Reporting.

- **Non-expedited Reporting:** Adverse events not requiring expedited reporting through CTEP-AERS should be entered into REDCap within 10 calendar days of learning of the event.
- **Expedited Reporting:** See Section 10.4 for CTEP-AERS expedited reporting.
- Site staff and/or Principal Investigators will also notify WF NCORP Research Base via REDCap reporting and report to CTEP-AERS within 24 hours of discovering the details of all **unexpected (possible, probable and definite) severe, life-threatening (grade 4) and all (expected or unexpected) fatal adverse events (grade 5).**
- All recorded adverse events reported to the Wake Forest NCORP Research Base will be reviewed by the Wake Forest NCORP Research Base Data and Safety Monitoring Committee (DSMC) and will be included in statistical reports to the Wake Forest NCORP Research Base Data and Safety Monitoring Board (DSMB).

Adverse Events								
	Grade 1 & 2		Grade 3		Grade 4		Grade 5	
	Expected	Unexpected	Expected	Unexpected	Expected	Unexpected	Expected	Unexpected
Unrelated						REDCap	REDCap & CTEP-AERS	REDCap & CTEP-AERS
Unlikely						REDCap	REDCap & CTEP-AERS	REDCap & CTEP-AERS
Possible				REDCap		REDCap & CTEP-AERS	REDCap & CTEP-AERS	REDCap & CTEP-AERS
Probable				REDCap		REDCap & CTEP-AERS	REDCap & CTEP-AERS	REDCap & CTEP-AERS
Definite				REDCap		REDCap & CTEP-AERS	REDCap & CTEP-AERS	REDCap & CTEP-AERS

The Wake Forest NCORP Research Base Multi-PI(s), the Wake Forest NCORP Research Base DSMC and/or Study Chair will take appropriate action to inform the membership and statistical personnel of any protocol modifications and/or precautionary measures, if this is warranted.

Institutions must comply with their individual Institutional Review Board (IRB) policy regarding submission of documentation of adverse events. All CTEP-AERS reports should be sent to the local IRB in accordance with the local IRB policies.

#### 10.4 Responsibilities of Local Sites for Expedited Reporting (CTEP-AERS)

Wake Forest NCORP affiliates and sub-affiliates (local sites) are required to notify the WF NCORP Research Base if a participant has an adverse event requiring expedited reporting by emailing [contact]. All SAEs that meet expedited reporting criteria defined in the reporting table below will be reported via CTEP-AERS, the Adverse Event Expedited Reporting System, accessed via the CTEP web site, <https://ctepcore.nci.nih.gov/ctepaers/security/login>.

**IMPORTANT:** When reporting in CTEP-AERS please ensure a copy of the report is sent to WF NCORP RB by adding [[contact]](mailto:[contact]) to the distribution list within the reporting system.

Any correspondence between CTEP-AERS and/or the FDA about a reportable SAE should be forwarded to [[contact]](mailto:[contact]) also.

Commercial reporting requirements are provided in the table below. The commercial agent used in this study is Ramipril (Altace®).

**Expedited reporting requirements for adverse events experienced by participants who are receiving study agent/intervention (including within 30 days of the last administration of commercial study agent/intervention) should be reported as follows:**

Attribution	Grade 4		Grade 5	
	Expected	Unexpected	Expected	Unexpected
Unrelated or Unlikely			CTEP-AERS	CTEP-AERS
Possible, Probable, Definite		CTEP-AERS	CTEP-AERS	CTEP-AERS

1) This includes all deaths within 30 days of the last dose of study agent with a commercial agent/intervention, regardless of attribution. Any death that occurs more than 30 days after the last dose of study commercial agent/intervention and is attributed (possibly, probably or definitely) to the agent/intervention and is not due to cancer recurrence must be reported according to the instructions above.
 
2) Submission of the on-line CTEP-AERS report plus any necessary amendments generally completes the reporting requirements. You may, however, be asked to submit supporting clinical data to the CTEP-AERS, CIRB or WF NCORP RB in order to complete the evaluation of the event.
				

For more information see:

[https://ctep.cancer.gov/protocolDevelopment/electronic\\_applications/docs/aeguidelines.pdf](https://ctep.cancer.gov/protocolDevelopment/electronic_applications/docs/aeguidelines.pdf)

In the rare occurrence when Internet connectivity is lost, a 24-hour notification is to be made to CTEP by telephone at [contact]. Once Internet connectivity is restored, the 24-hour notification phoned in must be entered electronically into CTEP-AERS by the original submitter at the site.

## 11. STUDY MONITORING

### 11.1 Data Management

Data management for this study will be done electronically using the following systems.

Informed consent document	REDCap
Protocol registration form	OPEN/REDCap
Surveys and Data Collection Forms	REDCap

REDCap is a secure, web-based, and easy to program forms and research database platform utilized by the WF NCORP for many research projects. This study will be using REDCap as the electronic data collection platform with electronic Case Report Form (eCRF) for multi-site studies.

### 11.2 Case Report Forms

Protocol-specific case report forms (CRFs) will be submitted electronically to the WF NCORP Research Base Data Management Center via REDCap. Refer to Appendix B for a data submission checklist, showing the specific forms that are needed for each study visit.

Do not submit study data or forms to CTSU Data Operations.

Do not copy the CTSU on data submissions.

### 11.3 Source Documents

Source documents are the original signed and dated records of participant information (e.g., the medical record, shadow chart) which may include electronic documents containing all the information related to a participant's protocol participation. Source documents are used to verify the integrity of the study data, to verify participant eligibility, and to verify that mandatory protocol procedures were followed. An investigator and other designated staff are required to prepare and maintain adequate and accurate documentation that records all observations and other data pertinent to the investigation for each individual participating in the study. All data recorded in the research record (including data recorded on CRFs) must originate in the participant's medical record, study record, or other official document sources.

Source documents substantiate CRF information. All participant case records (e.g., flow sheets, clinical records, physician notes, correspondence) must adhere to the following standards:

- Clearly labeled in accordance with HIPAA practices so that they can be associated with a particular participant or PID;
- Legibly written in ink;
- Signed and dated in a real time basis by health care practitioner evaluating or treating the participant; and
- Correction liquid or tape must not be used in source documents or on CRFs.

- Corrections are made by drawing a single line through the error. Do not obliterate the original entry. Insert the correct information, initial, and date the entry.

All laboratory reports, pathology reports, x-rays, imaging study and scans must have:

- Complete identifying information (name and address of the organization performing, analyzing, and/or reporting the results of the test); and
- Range of normal values for each result listed.

## 11.4 Data and Safety Monitoring Plan

In accordance with the NIH requirement, a Data Safety and Monitoring Plan (DSMP) has been established to guide the oversight of this study in order to ensure the safety of participants and the validity and integrity of the data. This monitoring will be commensurate with minimal risk present to participants.

The Wake Forest NCORP Research Base Data and Safety Monitoring Committee (DSMC) meets monthly to review reportable Adverse Events and Protocol Deviations to identify urgent safety and data concerns that may affect study safety and data quality. Adverse Event and Protocol Deviation reports are generated by the Wake Forest NCORP Research Base Data Management team. The DSMC consists of members of the Wake Forest NCORP Research Base team including one of the NCORP Research Base Multi-PIs, the Wake Forest NCORP Research Base Administrator, regulatory, and data team members.

The Wake Forest NCORP Research Base Data and Safety Monitoring Board meets every six months to review Wake Forest NCORP Research Base protocols. The Board includes members demonstrating experience and expertise in oncology, biological sciences, biostatistics and ethics. The DSMB report is generated by the Research Base statistician. Areas of review may include the following: Study Objectives; Patient Accrual; Patient Status and Retention; Study Status; Last Contact Status; Patient Compliance; Number of Biopsies/Labs as needed; Patient Characteristics; Summary of Observed Toxicities; Adverse Events; Date, Event briefly described, Relationship to Drug, Arm assigned; Summary of Primary and Secondary Measures.

**DSMB Responsibilities:** The DSMB reviews accrual information and interim analyses of outcome data and cumulative toxicity data summaries to determine whether:

- the trial should continue as originally designed
- the trial should be changed
- the trial should be terminated
- outcome results should be released prior to the reporting of the study results

Members of this committee as well as the organization statistician will oversee the safety monitoring of the study to ensure that the privacy of all participants in the study is protected; ensure that participants' interests are primary, that is, above the interests of the scientific investigation; and to ensure that all data collection is scrutinized for accuracy, privacy and levels of protection. The committee will perform reviews of the data handling and confidentiality and comply with recommendations to resolve such problems, and maintain written communication of the deliberations and recommendations that arise from their meetings. By examining this information, they will keep abreast of critical issues regarding recruitment and data integrity. Reports of all DSMB meetings and recommendations will be provided to the NCI, CIRB, WF NCORP RB, and participating sites, as requested.

## **11.5 Protocol Adherence**

Investigators ascertain they will apply due diligence to avoid protocol deviations. If the investigator feels a protocol deviation would improve the conduct of the study this must be considered a protocol amendment, and unless such an amendment is agreed upon by the Study PI and approved by the DCP, CIRB and any other stakeholders, it cannot be implemented. All protocol deviations will be recorded on the Protocol Deviation Log (see Appendix F) and also in REDCap.

## **11.6 Sponsor or FDA Monitoring**

The NCI, DCP (or their designee) or Wake Forest NCORP Research Base may monitor/audit various aspects of the study. These monitors will be given access to facilities, databases, supplies and records to review and verify data pertinent to the study. The use of the drug Ramipril in this protocol has been designated IND-exempt by the FDA and therefore does not require FDA monitoring.

## **11.7 Record Retention**

Clinical records for all participants, including CRFs, all source documentation (containing evidence to study eligibility, history and physical findings, laboratory data, results of consultations, etc.), as well as IRB records and other regulatory documentation will be retained by the Investigator in a secure storage facility in compliance with Health Insurance Portability and Accountability Act (HIPAA), Office of Human Research Protections (OHRP), FDA regulations and guidance, and NCI/DCP requirements, unless the standard at the site is more stringent. Wake Forest NCORP Research Base requires the records to be retained for at least 5 years after the study is discontinued and they should be notified prior to any planned destruction of material, unless the standard at the site is more stringent. NCI will be notified prior to the planned destruction of any materials.

# **12. STATISTICAL CONSIDERATIONS**

## **12.1 Study Design/Description**

### **Study Design/Endpoints/Hypotheses**

We propose a single arm pilot study to assess the feasibility of the use of Ramipril for GBM and the effect of Ramipril on neurocognitive function in patients using Ramipril in addition to standard chemotherapy and RT for GBM. Patients will receive once daily oral Ramipril to be taken at the start of RT and continue for four months after completion of RT. Outcome assessments will be made at 1- and 4-month post-RT. The results of our trial will be compared to those from the control group of RTOG 0825. The objectives for this trial are: 1) to assess the retention rate of patients at 10 weeks of Ramipril treatment (6 weeks during RT and 4 weeks post RT) defined by compliance with drug therapy for at least 75% of doses during the 10 week period and completion of the composite neurocognitive battery, 2) to estimate the effect of 10 weeks of Ramipril on neurocognitive function in patients with GBM receiving chemoradiotherapy as measured by the Clinical Trial Battery Composite (CTB COMP) score, 3) to estimate the time to neurocognitive decline as assessed by the Clinical Trial Battery Composite (CTB COMP) score, 4) to estimate the effect of treatment on specific non-memory cognitive functions including attention, executive function, visuo-motor skills, working memory, a screening measure of global cognitive function, mood, quality of life, fatigue and sleep disturbance, 5) to collect preliminary

data on the presence of apolipoprotein epsilon (ApoE) isoform 4 serum (peripheral blood lymphocyte) test positivity as measured by quantitative PCR, and 6) To estimate neurocognitive function in surviving patients at the 4 month post RT endpoint. We will also explore differences in 4 month post RT outcomes by whether the patient received Optune® (also known as Tumor-Treating Fields or TTFields) as part of their standard treatment following RT.

Study hypotheses that will be explored include the following: 1) patient retention will be sufficiently high to proceed forward with a randomized trial of Ramipril; 2) patients receiving Ramipril will have better neurocognitive function (assessed using the Clinical Trial Battery Composite Score) compared to historical controls who did not receive Ramipril; 3) neurocognitive decline will be slower in patients receiving Ramipril; 4) patients receiving Ramipril will have better scores for the individual neurocognitive function tests; 5) patients receiving Ramipril will have better mood and quality of life and less fatigue and sleep disturbance.

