### 1.2 Secondary Objectives

- 1.2.1 To estimate the time to neurocognitive decline with GBM receiving chemoradiotherapy and Ramipril. Decline will be defined as the time at which a change greater than the reliable change index for any of the individual cognitive tests is experienced for a particular patient.
- 1.2.2 To estimate the effect of treatment with Ramipril on and variability of specific non-memory cognitive functions including attention, executive function, visuo-motor skills, working memory, a screening measure of global cognitive function, mood, quality of life, fatigue and sleep disturbance.
- 1.2.3 To collect preliminary data on the presence of apolipoprotein epsilon (ApoE) isoform 4 serum (peripheral blood lymphocyte) test positivity as measured by quantitative PCR.
- 1.2.4 To estimate neurocognitive function in surviving patients at the 4 month post RT endpoint.
- 1.2.5 To estimate response as reported by treating physician assessments.

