Optune® with adjuvant temozolomide in patients with newly diagnosed supratentorial glioblastoma is listed as a level 1 recommendation by the NCCN guidelines and has been adopted by many, but not nearly all, medical practitioners who treat these patients. Currently, a minority of newly diagnosed glioblastoma patients are either offered or choose to accept this treatment modality due to patient or provider preferences, or established contraindications to use which include the presence of implantable electronic devices, allergy to the array’s conductive hydrogel adhesive or the presence of cranial defects. Optune® may only be prescribed by qualified physicians who have completed a training course given by Novocure (the device manufacturer). Of note, as prescribed in the pivotal clinical trial referenced above, standard practice is to apply the Optune® device no sooner than 4 weeks after the completion of concurrent radiation and temozolomide chemotherapy.

For patients enrolled on this trial, Optune® may be used at the discretion of the treating physicians as per standard of care guidelines, timing and training. Use will be captured and an exploratory analysis of primary and secondary objectives based on the subgroups using and not using the device will be performed.

**Drug:** Ramipril (e.g. Altace® or Tritace®) is an ACE-I. It is currently FDA approved for use in the treatment of hypertension and for reducing the risk of myocardial infarction, stroke and death from cardiovascular causes. The drug will be obtained, packaged, and distributed by McKesson Corporation (Winston-Salem, NC). McKesson Corp. will also provide storage and inventory for the study drug. Ramipril will be provided to study participants at no cost.

**Assessment plan:** Participants will complete the entire battery of neurocognitive tests and questionnaires measuring cognitive symptoms, mood, fatigue, sleep disturbance and quality of life at baseline, at the completion of RT, 1 month post-RT, and q3 monthly thereafter up to 4 months post-RT or until time of

tumor progression. At the end of radiation and at the one and four-month post-RT follow-up visit, patients' tolerance of medication and compliance will be assessed by a research team member at an in-person visit coordinated with clinical follow-up. Patients are encouraged to call at any time for questions regarding study drug and will fill out a diary to document study drug compliance.

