## 8. CRITERIA FOR EVALUATION AND ENDPOINT DEFINITION

### 8.1 Primary Endpoints

**Retention rate at 10 weeks of treatment (6 weeks during RT and 4 weeks [1 month] post RT):**

Retention will be defined as compliance with drug therapy for at least 75% of doses during the 10 week treatment and completion of the composite neurocognitive battery as detailed below.

**Neurocognitive performance measured by the Clinical Trial Battery Composite (CTB COMP) score at 10 weeks of treatment (6 weeks during RT and 4 week [1 month] post RT):** Tests have been selected to represent a range of functions affected by cancer and RT including attention, memory, working memory, executive functions and verbal fluency. All cognitive testing will be performed by trained and certified research staff. Proposed neurocognitive measures are: Hopkins Verbal Learning Test-Revised (HVLT-R Delayed Recall; 5 min); Trail Making Test A & B (TMT; 8 min) and Controlled Oral Word Association test (COWAT 3 letters; 5 min). The composite neurocognitive score is defined as the arithmetic mean of the standardized scores from the HVLT-R total recall, HVLT-R Delayed Recall, HVLT-R Delayed Recognition Discriminability (all portions of the HVLT-R delayed recall), Trail Making Test Part A, Trail Making Test Part B, and COWAT. We will assess the effect size in terms of the composite neurocognitive score.

The entire battery of neurocognitive tests and questionnaires will take approximately 38 minutes to complete. We have used a similar battery successfully in two phase 2 studies and one phase 3 study involving breast and brain tumor cancer survivors. Data completeness in those studies was over 95%.

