#### 8.3.1 Off-Agent Criteria

Participants may stop taking study agent for one or more of the following reasons: completed the protocol-prescribed intervention, adverse event (AE) or serious adverse event (SAE), inadequate agent supply, refusal to continue with study procedures, the need for contraindicated concomitant medications, medical contraindication, disease progression, death or treating physician decision.

Date and reason off-agent should be documented on the Off Agent case report form. Reasons that are not specified on the form should be coded as 'Other' and a brief description provided. Patients who go off-agent must be followed for adverse events (AEs) for at least 30 days from their last treatment.

Note that participants who go off-agent should be encouraged to stay in the study and provide data at the regularly scheduled visits. Local NCORP site staff should complete the study assessment with the patient, especially the neurocognitive and PROs testing and toxicity assessments. LabCorp samples do not need to be collected once the patient is "Off Agent.". Local institutional labs can be used to assess the participant after they are off Ramipril.

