Treating physician response rate will be summarized at each timepoint with corresponding 95% confidence intervals. Time to neurocognitive failure will largely follow the method reported in Gilbert *et al.* for evaluating if there is meaningful difference in the risk of cognitive progression. Neurocognitive failure will be defined as the first decline on reliable change index on any of the individual cognitive tests. In the presence of competing risks for neurocognitive failure, including GBM-related mortality risk, we plan to explore the use of competing risks methods for both descriptive statistics (e.g. the Kaplan-Meier curves) and competing risk regression analysis. Competing risk methods are needed because time to neurocognitive failure is not independent of mortality and ignoring events from competing risk will lead to biased results. The competing risk analysis will be based on the method proposed in Gray and Fine and Gray using SAS macro %CIF and PROC PHREG. Patient reported outcomes will be assessed as described above for the CTB COMP.

Exploratory subgroup analyses will be conducted for all 4 month post RT outcomes by whether the patient received Optune® (also known as Tumor-Treating Fields or TTFIELDS) as part of their standard treatment following RT. Differences by Optune® for continuous outcomes will be assessed by two-sample t-tests where parametric assumptions hold; otherwise Mann-Whitney U tests will be applied. For categorical outcomes, Fisher's exact or Chi-square tests will be implemented. Corresponding 95% confidence intervals will also be presented for outcomes within each subgroup.

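### Section 12.1 times neurocognitive decline on the composite score while 1.2.1 and 12.4 time it on any single test, and the sections disagree on cognitive testing after progression

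*Combined protocol and SAP*

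**What the plan says.** **Definition of decline.** Section 12.1, objective 3, is "to estimate the time to neurocognitive decline as assessed by the Clinical Trial Battery Composite (CTB COMP) score". Section 8.1 builds that composite as a mean: "The composite neurocognitive score is defined as the arithmetic mean of the standardized scores from the HVLT-R total recall" and five further scores. No section gives a threshold for decline on it. Objective 1.2.1 uses "a change greater than the reliable change index for any of the individual cognitive tests". Section 12.4 agrees with 1.2.1: "Neurocognitive failure will be defined as the first decline on reliable change index on any of the individual cognitive tests".

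**Testing after progression.**
- Section 3 (assessment plan) schedules the battery at baseline, at the end of RT, at 1 month post-RT, and "q3 monthly thereafter up to 4 months post-RT or until time of" tumor progression.
- Section 8.3.1 lists disease progression among the reasons for stopping study agent, and then says "participants who go off-agent should be encouraged to stay in the study and provide data at the regularly scheduled visits".
- Section 7.1 note E and the Off Agent entry in 7.3 also keep assessments going after study agent stops, unless the patient is unwilling or withdraws consent.
- Section 8.3.2 lists disease progression as a reason a participant may leave the study altogether.
- Section 7.3 asks for the next neurocognitive set when a patient leaves the study for any reason.

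**Competing risks.** Section 12.4 plans competing-risks methods for "descriptive statistics (e.g. the Kaplan-Meier curves") and for regression. It warns that ignoring competing events biases the result, and names the %CIF macro and Fine-Gray regression. It names GBM-related mortality as a competing risk and does not say how progression is handled.

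**The concern.** A mean of six scores and the worst of six scores respond to different things. The mean dilutes a fall confined to one domain. The any-test rule catches that fall, but gives measurement error six chances per visit. An analyst working from 12.1 and one working from 12.4 would therefore report different event rates for the same patients, and these estimates are meant to inform the design of a randomized trial.

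The testing rule decides which data exist. If some sites stop at progression and others continue, Week 22 scores are missing in a pattern tied to progression, which is plausibly related to cognition, and to site habit. That affects time to decline and the 4-month cognitive outcomes.

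On the descriptive curve, one minus Kaplan-Meier with deaths censored overstates the incidence of decline when death competes. This is the bias that Section 12.4 itself warns about.

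**Working it through.** **1. The plan's own figure.** The only sample-size figure is for retention (Section 12.2: null 65%, alternative 80%, one-sided 0.05, 90% power).

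n = [1.645·√(0.65·0.35) + 1.282·√(0.80·0.20)]² / 0.15² = 74.78, rounded up to 75.

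This reproduces. The exact rule of at least 56 of 75 retained has a one-sided error of 0.0485 and power 0.900. Nothing in it uses the definition of decline.

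**2. One visit, stable patient.** Take six independent scores, each judged by its own RCI in the direction of decline.
- Cut-off 1.645 (tail 0.05): 1 − 0.95⁶ = 26%, against 5% for a composite judged by its own RCI.
- Cut-off 1.96 (tail 0.025): 1 − 0.975⁶ = 14%, against 2.5%.
- If the HVLT-R counted once, leaving four tests: 1 − 0.95⁴ = 19% at 1.645.

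**3. Three follow-up visits (Weeks 6, 10 and 22), stable patient.** The simulation used 200,000 patients per setting and measurement error only. For each score, z = (follow-up − baseline)/√2. Errors have correlation ρ between scores and are independent between visits. The composite z is the mean of the six z values divided by √((1+5ρ)/6). A patient is flagged if z falls below minus the cut-off at any visit.

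| ρ | Any test, 1.96 | Composite, 1.96 | Any test, 1.645 | Composite, 1.645 |
|---|---|---|---|---|
| 0 | 32% | 6% | 53% | 12% |
| 0.4 | 25% | 6% | 41% | 12% |
| 0.6 | 21% | 6% | 34–35% | 12% |

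At ρ = 0.4 the two rules classify roughly 20% (1.96) or 30% (1.645) of stable patients differently.

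**4. With true change.** The settings are cut-off 1.645, three visits, correlation between scores 0 to 0.7 and between visits 0.5. Shifts are in standard errors of the difference.
- One score down by 2: the any-test rule flags 86–92%, the composite 22–39%.
- All six scores down by 0.5: 55–84% against 30–57%.

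The cut-offs, the correlations and the composite's own RCI are assumptions; the documents give none of them. The any-test rate was the higher in every setting tried.

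**5. A patient who progresses after Week 10 and stops study agent.**
- Section 3: no Week 22 battery.
- Sections 8.3.1, 7.1 note E and 7.3: Week 22 battery if the patient is willing.
- Section 8.3.2, if the patient is taken off study: one further set on leaving (7.3), and then nothing at Week 22.

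One patient can thus yield three different data records, and Section 12.4 does not say how any of them enters the time-to-decline analysis.

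**The case against.** **Only one definition can be run.** Objective 1.2.1 and the analysis plan agree, and 12.1 is a one-line restatement without a threshold. This stands. A reader might infer two evenly matched definitions, but the documents favor the any-test rule, and correcting one phrase resolves the mismatch.

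**The primary endpoint is not shown to suffer.** A reader might infer that anyone progressing before Week 10 fails retention by design. The text does not support that. Section 3 lists the 1-month battery separately, and its progression clause most naturally limits only the later visit. After baseline, scheduled imaging falls at Weeks 10 and 22. A patient leaving the study is due one further battery, although the plan does not say whether it counts as the Week 10 battery. Earlier progression found off schedule could matter: if true retention fell from 80% to 78%, power under the exact rule would fall from 90% to 80%. The documents give no rate for such cases, so this stays conditional.

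**Missing data are already addressed.** Sections 12.4 and 12.5 plan multiple imputation under varied missingness assumptions and a propensity-to-be-missing analysis. These reduce the problem. They do not replace scores that a site never collected because it read Section 3.

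**The Kaplan-Meier wording is a loose example.** Largely so. A reader might infer that the plan will report one minus Kaplan-Meier, but the same paragraph names %CIF and Fine-Gray. What remains is a wrong example to correct.

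**The fix adopts the noisier rule.** True. The rule is nevertheless the one in the stated objective and the analysis plan. Section 12.4 ties it to a previously reported method, apparently that of the bevacizumab trial that supplies the controls. Comparison with those controls needs the same rule on both sides, and the composite version then serves as a check.

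**Conclusion.** The point holds as a set of inconsistencies in a secondary, estimation-only endpoint. The two definitions are materially different: about 21–53% against 6–12% of stable patients flagged by Week 22. Those figures show direction and range only, because they rest on the assumed cut-offs and correlations.

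They should not be set against the background figure in Section 2.1 of about 30% significant decline within four months, as if noise and signal were on one scale. That figure is not tied to either rule.

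The conflict over testing after progression is real and involves Section 8.3.2 as well as Section 3. Its main effect is on Week 22 data. No size can be given, because the documents state no progression rate. The Kaplan-Meier point is small, and the documents give no death rate from which to size it. The retention test and N=75 stand.

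**What to change.** 1. In Section 12.1, objective 3, replace the composite with the any-test RCI definition of 1.2.1 and 12.4. Name CTB COMP decline as a sensitivity analysis with its own threshold. In 12.4, state the RCI cut-off and which scores count as individual tests.
2. In Section 12.4, replace the Kaplan-Meier example with the cumulative incidence function, with death as the competing event.
3. Reconcile Sections 3, 7.1, 8.3.1 and 8.3.2 so that cognitive testing continues after progression in willing patients. Removing the progression clause from Section 3 is not enough, because 8.3.2 would still allow exit at progression.
4. In Section 12.4, state how progression and later scores are handled. Add a sensitivity analysis cut at progression, in case RTOG 0825 stopped testing there; the documents do not say whether it did.

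The cost is protocol and SAP wording, plus a few extra assessments in patients who have progressed, which 8.3.1 already encourages. The sample size does not change.
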